Existing COVID-19 testing and prevention strategies are failing many communities in the United States.¹ COVID-19 testing uptake, social distancing, contact tracing, all face significant acceptability and implementation challenges among those most impacted in the US.² COVID-19 testing has had technical and diagnostic challenges since its inception; however, these challenges are overshadowed by significant implementation challenges. First, messaging of testing importance is complicated because of stigma related to subsequent social isolation, employment loss and potential illness and death.^{3,4} Second, testing has been perceived by many community members to be futile. In C3 focus groups, participants have described that it is not safe to go out and seek testing without private transportation and further there is no reason to test as there is nothing that can be done (July 2020 C3 FGD, Chicago). Third, messages about the importance of testing are most often delivered by public health authorities. These messages (and the messenger) do not resonate with community who often are facing significant racism/stigma, lack resources to meet basic needs, and structural violence in the form of law and immigration enforcement.⁵ Finally, community members who are disenfranchised from health insurance are concerned about costs of testing or that their data will be used by government. Because of these factors, community faces significant real and perceived barriers to testing.^{2,5}

The distribution of COVID-19 vaccines faces similar challenges. Although COVID- 19 vaccine acceptance is slowly increasing across all demographic groups, vaccine confidence still lags behind in Black and Hispanic communities⁵⁰ First, structural violence, historical trauma, and sustained inequality largely shape medical mistrust in those who are experiencing health disparities¹⁰. Within the United States' context, the medical establishment has a long history of exploiting people of color - specifically black, Latinx, and Indigenous individuals - for the sake of purported medical advancement⁵¹ . The case of Henrietta Lacks, the Tuskegee Studies, and the experiments of James Marion Sims upon Lucy, Betsy, and Anracha are just a few examples of the historical medical trauma exerted upon Black and African American individuals living within the United States⁵¹ A strong predictor of intention to get vaccinated is confidence in vaccine safety and effectiveness⁴⁹ Second, there are concerns around vaccine side effects and concerns about getting COVID-19 from the vaccine⁵⁰ Finally, vaccine misinformation ranging from rumors to conspiracy theories is contributing to the mistrust around eth COVID-19 vaccines, making it challenging to build confidence around vaccines⁵²

COVID-19 has disproportionately impacted disenfranchised communities.⁶ Disenfranchisement is a status that results in distrust of public institutions and therefore individuals do not participate in services, resources, and benefits.^{7,8} Disenfranchisement generates, maintains, and propagates vulnerability both directly and indirectly.^{7,9} Poverty, limited opportunity for prevention or other health services and racism all contribute to the COVID-19 inequities that are similar in magnitude to other socially determined outcomes, such as kidney disease, violence and death due to AIDS.^{10,11} Two key disenfranchised populations where significant COVID-19 transmission occurs is among criminal justice involved (ie. arrest, history of jail/prison, probation/parole) and low-income Latinx community members.^{6,11,12,13,14} Both of these populations, and the overlap between them, have some of the highest rates of COVID-19 infection and death in the US.^{13,15} These stark COVID-19 inequities are driven by several factors that the communities share.¹⁵ First, both are often disenfranchised from employment, social services and health-care, all critical to supporting those impacted most by COVID-19. In addition, if employed, most are part of the essential low-wage workforce where transmission is high, and frequent outbreaks occur within multi-generational working households.^{12,16,17} There often can be limited agency and self-determination in such contexts (ie. inability to self-isolate) which can be disempowering and thus requires interventions that are self-affirming. Finally both CJI and Latinx communities often have considerable distrust in institutions including public health¹⁸ and lack access to accurate and contextually/linguistically appropriate COVID-19 information.¹⁹ Misinformation around testing and vaccination impedes efforts to effectively engage these communities.^{10,20,50} Therefore, we utilize theory-driven self-affirming message framing

as well as misinformation correction in order to fully engage communities around COVID-19 testing and vaccination.^{11,21-23}

Criminal justice involved populations include diverse non-incarcerated people with history of arrest/jail/ prison, community supervision (probation/ parole), mandated drug court attendance and are susceptible to distrust in public health institutions. One in five American adults has had justice exposure including arrest, incarceration, being on supervision, and/or being subjected to a number of liberty restrictions including the right to vote, right to live with family members, and employment limitations.²⁴ CJI populations' differential experiences with justice systems, and other social institutions like child welfare and Medicaid, impact willingness to engage in testing. In NIDA's first JCOIN data product developed by the C3 team we used NORC's AmeriSpeak Panel,²⁵ a probability-based panel of about 35K households designed to be representative of the US to examine COVID-19 among CJI people. We found that respondents with a history of CJI are 18x more likely to have a household member pass away from COVID (9% to 0.5%) than those without such history. Those respondents with a history of CJI are also less likely to be able to follow important preventative health measures recommended for COVID-19 (e.g., wearing a mask, social distancing). Complicating these relationships are that CJI individuals are more likely to have higher rates of legal cynicism and perception of procedural injustice which affect trust in social institutions. Legal cynicism often translates into anti-authority attitudes that affect willingness to engage in health or self-care activities, and given the higher rates of substance use, mental health, and infectious diseases among CJI populations,^{26,27} COVID-19 testing and vaccination promotion messaging must be tailored to address the justice experience, distrust of justice agencies, and self-efficacy.

Low-income Latinx people (250% at or below FPL) have some of the highest rates of COVID-19 in the US and require testing interventions that address unique cultural factors and engage familial support systems. Latinx and Hispanic people (hereafter Latinx) include a diverse set of communities and several intersectional factors: country of origin, duration of time in US, and documented status. Nearly 25% of Latinx people are employed in essential service industries²⁸ (e.g., food service, factory processing) and are exposed to a greater likelihood of contracting COVID while working.²⁹ Additional barriers to consider for non-citizens are that they are more likely to experience barriers to social distancing due to household size,³⁰ and few roles in the low-wage, essential workforce have the option to work fully or even partially remotely. Latinx are also more likely to have three generations reside in a household,³¹ which requires different approaches to promote public health messages for testing and preventing the spread of COVID-19 within a household. Latinx who are undocumented or who are in mixed-status households are more likely to be uninsured and less likely to access and utilize healthcare services³² including COVID-19 testing. The existence of multi-generational and other mixed-status households are examples of the collectivistic culture that places a prominent role on *familismo*, which is an important protective factor for an individual's well-being.^{33,34} Family network based approaches that integrate household members play a critical role in promoting well-being for oneself as well as others.³⁵ The social network strategy is an example of a testing approach that can leverage existing family network structures to promote and engage even the most marginalized communities in testing and vaccination.

The Social Network Strategy (SNS) was developed for HIV and is adapted to accelerate COVID-19 testing to identify networks most at risk. Social network interventions are recognized as highly potent testing interventions that move beyond individual-level "risk"³⁶ which are key to COVID-19 elimination efforts. Network mobilization/induction is a Type III intervention strategy that stimulates peer-to-peer interaction to create behavioral diffusion through existing social pathways among network members.³⁷ This Type III intervention represents a class of network interventions that have been found to be effective in HIV prevention (i.e., CDC's EBI—Social Network Strategy).³⁸ Past research has shown that individuals who are members of the same social network are more likely to have similar HIV risk potential.³⁹ SNS identifies HIV positive individuals and/or individuals at risk for acquiring HIV and motivates them to recruit persons from their social network for testing and provides modest compensation for referrals. In so doing, the reach of the testing program increases as does the volume of people tested. In a recent study conducted by members of C3,⁴⁰ the social network strategy (SNS)

was superior in HIV case identification when compared to standard testing approaches, such as those in health care settings (i.e. emergency department) or contact tracing. These findings are not surprising given that social network theory, such as homophily (i.e. birds of a feather)⁴¹ suggest that subsequent waves of referred network members will resemble an index client's attributes.

STUDY DESIGN

The scientific premise of C3 is to engage disenfranchised people in COVID-19 testing and vaccination referral through social network referral combined with theory-driven COVID-19 prevention messaging. Eligible CJI and Latinx clients (and the overlap between the two) will be enrolled into C3.

Using a two-arm randomized controlled trial design, participants will be enrolled into the SNS arm (involves social networking referrals only) or the SNS+messaging arm. The latter includes affirmation/misinformation correction messaging (discussion tools and coaching). SNS and SNS+messaging arms will both include an initial group of index study participants who will refer their network members into the study and the process will repeat itself one more time for a total of 3 waves.

Capitol Area Reentry Program (CARP) Baton Rouge, LA	[name]	University of Chicago IRB	Orleans Health Dept.	CJI, substance users	250	Implementation science
University of Texas SW Dallas Cnty., TX	[name]	University of Chicago IRB	Parkland Hospital	Latinx	600	Predictive analytics, vulnerability index, COVID-19 testing
San Jose State University Santa Clara Cnty., CA	[name]	University of Chicago IRB	NA	Latinx	NA	Health Inequities, Intersectionality, and Infectious Diseases
GMU Fairfax, VA	[name]	University of Chicago IRB	NA	NA	NA	Health Inequities, Intersectionality, and Infectious Diseases
NORC	[name]	University of Chicago IRB	NA	All	NA	Study design and planning, Site management and training, Data analysis

Test intervention efficacy (numbers tested - COVID-19 test results will be collected as part of study data; numbers vaccinated – COVID-19 vaccine records will be collected as part of the study) and community factors that may moderate efficacy. Secondary analysis to compare numbers tested in SNS strategies and COVID-19 contact and determine whether COVID-19 status within social networks impacts the referral process.

STUDY SITES

This multi-site study will be completed at eight sites as shown in Table 1. Upon IRB approval, these sites will participate in research activities as listed in Appendix A, including recruitment, participant engagement and interviews. In-person study activities will be conducted by IRB approved study staff and faculty at the study center shown in Table 1, or in a private room at a public library or school. If the study interaction takes place in a public library or school, study activities will be conducted by IRB approved study staff who will ensure that subjects have complete privacy including that the room has a door and there are no other people present except for the subject and the study staff member, unless the Messaging Intervention (described below, number 4 under Study Visit Procedures) is being delivered, which can occur as a small group of consented subjects.

University of Chicago will provide pre-programmed tablets to all study sites. These tablets have been programmed by the Research Computing Group within the Department of Public Health Sciences (leadership [name]) at the University of Chicago to ensure data protection and enable data transfer. All data collection will be conducted electronically via tablets and data will be uploaded into databases hosted by University of Chicago. These are similar procedures as have been developed with [name] for NIDA's Methodology and Advanced Analytics Research Center (PI [name]).

The University of Chicago BSD IRB will act as IRB of Record for all sites, except Indiana University (due to their enrollment of juvenile CJI populations) who will use their own institutional IRB.

METHODS

AIM: Test intervention efficacy (numbers tested – COVID-19 test results will be collected as study data; numbers vaccinated – COVID-19 vaccine records will be collected as part of the study) and community factors that may moderate efficacy. Secondary analysis to compare numbers tested in SNS strategies and COVID-19 contact and determine whether COVID-19 status within social networks impacts the referral process.

We hypothesize that participants randomized to receive SNS+ (SNS+COVID-19 messaging) will be more likely to have their network members successfully tested and vaccinated (study participants will be given COVID-19 vaccine information and contact information to vaccination sites in their community. Vaccination will depend on the network members' tier/health department eligibility for vaccination). We also hypothesize that both SNS and SNS+ will generate more people tested per index as compared to COVID-19 contact tracing. Finally, we anticipate that there may be differential intervention effects across sites, by CJI status, prior COVID-19 testing history, race/ethnicity, and network composition, and will formally evaluate these differences as part of analyses.

Recruitment of Index and Network Member study participants.

We will enroll index seeds (12% of sample) ages 18 and over who are CJI or low-income Latinx across eight collaborative sites. Index clients and their social network referrals will be recruited by local Research Assistants (RAs) embedded within community-based agencies and community health care settings that provide a number of in person and remote social and care services, including community COVID-19 testing.

Recruitment activities may include:

- In-person recruitment may be conducted at the study center (Table 1), during regular drop-in and community-based services, and events occurring at the study center and its outreach programs. This may include providing a study flyer or contact card so that a client can contact the study team directly about participation. A sign-up sheet may also be provided, where interested clients can provide their contact information if they wish to be contacted by the study team about the study.
- Flyers posted at study centers
- Social media postings
- Contacting individuals from previous studies who have indicated interest in being contacted for future work or from existing community programs.

Subjects will also be recruited through other study participants through compensated referral. Each study participant will be given a referral code that will be used for identification purpose. The study participants will distribute flyer and the referral code to people who are eligible for the study. People who are eligible and provide the referral code can be enrolled in the study. Participants will also be recruited from participants in other studies who have agreed to be contacted for future studies.

A two-step referral process will be utilized whereby index seeds will refer 308 first- and second-degree social network members (88% of sample). So indexes will refer network members (1st degree) and then those network members will refer one more round (2nd degree). Index seeds will meet the eligibility for index community members while the first and second-degree network members will meet the social network member eligibility (see inclusion and exclusion criteria below). Based upon previous experiences with SNS recruitment, we expect on average two social network members to be referred per study participant.

Each study participant will be given a referral code that will be used for identification purposes. The study participants will distribute the referral code to their network members who are eligible for the study. People who

are eligible and provide the referral code can be enrolled in the study. Network members will also have the option to bring others into the study visit with them or link them to the RA at a study site that is recruiting for this study.

Site specific details are listed in Appendix A, including recruitment plans, consent activities and overall study conduct for each site.

Inclusion and exclusion criteria

Index community members will be:

- (1) 18 years or older;
- (2) spend majority of their time in the metropolitan area or county where recruited;
- (3) have access to a phone for 21-day follow-up call; and
- (4) primary communication in English or Spanish (based on site chart above) AND at least one of the following:
 - (i) ever had CJI (operationalized as any jail, prison, arrest, parole (completed), probation, drug court);
 - (ii) ever had negative interaction with police or law enforcement that did not lead to an arrest or jail/prison time (operationalized as ever stopped, searched, physically or verbally abused, or had another negative interaction with police or law enforcement);
 - (iii) ever witnessed a negative interaction with police or law enforcement (operationalized as ever witnessed another person being stopped, searched, or physically or verbally abused by police or law enforcement);
 - (iv) lower-income Latinx (operationalized as at or below 250% of FPL).

Social network referrals will be:

- (1) linked to the index as a “friend, family, coworker or someone you spend time with on a regular basis”;
- (2) visit within two weeks of index visit;
- (3) 18 years or older;
- (4) spend the majority of their time in the metropolitan area or county where recruited;
- (5) have access to a phone for 21-day follow-up call; and
- (6) primary communication in English or Spanish (based on site chart above).

[figure not shown]
Exclusion criteria include:

- (1) inability to provide informed consent; and
- (2) active COVID-19 symptoms per CDC. Participants with COVID-19 symptoms will be referred for free testing at existing partners for each of the study sites.
- (3) currently on parole

Study Visit Procedures

All study participants (index and referral) will go through the following study procedures (Figure 4) include:

- Informed consent;
- Day 1 survey;
- Randomization;
- Messaging intervention (for SNS+ only);
- COVID-19 testing
- Social Network referral
- Day 21 Follow-up

1. **Informed Consent.** Eligible participants will be asked to participate in written informed consent using either a paper consent or electronic consent. The following consent processes applies to both the study consent form and the release of information form.

Paper Consent in-person:

A study team will provide the subject with a copy of the study consent. The consent document will be reviewed and any questions regarding the study will be answered by the study team. If the subject agrees to participate in the study, they will be instructed to sign the consent form. The subject will be provided with a final signed copy. A signed copy will be stored by the study team.

Electronic Consent in-person:

Consent may be obtained in-person electronically via RedCAP. Study staff can present the consent to the subject on the tablet or on paper depending upon subject preference. The consent document will be reviewed and any questions regarding the study will be answered by the study team. If the subject agrees to participate in the study, the subject will be instructed to sign the consent form via RedCAP e-consent signature. Staff will also sign the consent form and update the RedCAP link to provide the subject with a final, signed version of the consent form via email. The final signed consent document will be stored in RedCAP.

Electronic Consent Remote, using RedCAP:

Remote consent would be conducted via telephone or video call (with preference being video call whenever possible) using a link through REDCap. A link to the to the consent in RedCAP will be sent to the subject via text and/or email. The study staff will discuss the consent form with the subject, and any questions regarding the study will be answered by the study team. The subject's identity will be verified as described below. If the subject agrees to participate in the study, he/she will be instructed to sign the consent form via RedCAP e-consent signature. Staff will also sign the consent form and update the RedCAP link in order to provide the subject with a final, signed version of the consent form. The final signed consent document will be stored in RedCAP.

The study team will do due diligence to verify the subject's identity before beginning the consent process. Traditional means of verifying subject identity may be challenging in this subject population. Most will not be patients with local medical records to reference, some will not have formal state IDs, some may not have permanent residence, etc. Strict enforcement of state ID could disenfranchise those who may well be the most important group to reach and the very population that needs to be studied. Subject identity will be verified using the following methods, in the following order of requirement:

- 1) Visually display a driver's license or state ID

- 2) Visually display an alternative photo ID (employee ID, school ID, etc) in combination with a piece of mail displaying the subject's name.
- 3) Visually display an alternative photo ID (employee ID, school ID, etc) alone
- 4) Visually display one of the following pieces of mail with subject's name and address: utility bill, cellphone bill, correspondence from the secretary of state or other government organization
- 5) Visually displaying any piece of mail listing the subject's name and address
- 6) Asking the subject to verbally state their name

2. **Day 1 Survey.** Following consent, study participants will complete an electronic survey that includes social network inventory. Identifying information of social network members (first name and last initial and cross streets/zipcode/neighborhood) is collected through self-report for the purposes of connecting social networks of study subjects. Day 1 Survey is found in Appendix B. This will survey will be completed on the day of recruitment and will take 60 minutes. The RA can interview participants who have difficulty self-administering the survey.
3. **Randomization.** Will occur following the survey, and participants in the SNS+messaging arm will receive the messaging intervention (discussion tools and coaching). Study participants will be randomized to receive no messaging (i.e., SNS only) or SNS+messaging with equal probability. Randomization will be performed at the participant level, meaning that in general, participants within a recruitment cluster will be assigned to different groups. Random assignments will be provided by the University of Chicago via a web-based API, with the touchpads programmed to retrieve an assignment at the appropriate time and deliver the messaging (or not), as appropriate.

Indexes and first-degree referrals will be randomized as described above. Second-degree referrals will also be randomized, however, we will not ask for additional SNS referrals from them if the study sample size has been reached.

4. **Messaging Intervention.** Study staff will be notified of group allocation and provide the in-person message reinforcement and will address questions related to messaging.
 - a. ***C3 Study Conditions.*** Trained community engagement coordinators (CEC) that exist across C3 sites will deliver the study conditions. The CECs will have capacity to support multiple participants simultaneously in the self-administered portion of the study visit: clarifying any survey items, troubleshooting any technology/data collection issues, and transitioning to interviewer administered for people with limited literacy. CECs will provide the appropriate scripted messaging strategy based upon condition assignment (see conditions below) and will follow with describing and motivating the SNS network referral process.
 - b. ***SNS Study Condition.*** Study participants in the SNS condition will receive the SNS intervention training which will take about 30 minutes. This will occur towards the end of the study visit when CEC staff describe the SNS, construct a plan for successfully referring network members into the study, and discuss compensation for the recruitment efforts. CECs will specifically discuss network members of interest: "friend, family, coworker or someone you spend time with on a regular basis". Walkthrough and scenario play will be strategies to assist with planning regarding: (1) how the conversation will be raised, (2) how potential barriers to testing will be addressed, (3) how the screening by phone or web survey will be conducted, (4) what information about the study will be shared. Information from the client providing referrals will be kept confidential. Participants will be compensated \$20 per successful test completed per network member and up to six referrals, consistent with our previous work.⁴²
 - c. ***SNS+Messaging Condition.*** The SNS+ condition will include everything described in the SNS condition above. In addition, a scripted message (Appendix C) in the participant's preferred language

will be deployed via the tablet in written or audio format. Training for this additional messaging will take about 15 minutes.

- d. *Quality Monitoring* - A sample (5%) of the trainings will be recorded (video and/or audio) for quality improvement purposes. These recordings may be shared amongst the respective sites-specific study team (not shared outside of the subject's study site). Subjects will be asked whether they are willing to have the session recorded and can indicate yes or no on the study consent form.

- 5. **COVID-19 Testing**. All study participants, irrespective of symptoms, will be tested for COVID-19. Based on routine practices of the site, testing will be either administered by a clinical professional or conducted through self-administration according to CDC guidelines (Appendix I). Testing procedures will follow existing SOPs utilized at each site, utilizing FDA-approved tests. COVID testing at these sites is covered by public health programs for each site.

Test result provision will be provided by the testing/clinical team. All subjects will be provided with the CDC's information page "What Your Test Results Mean" (Appendix J).

- 6. **COVID-19 Vaccination**: All subjects will be provided with the link to CDC's COVID-19 vaccine information page "Key Things You Need To Know About COVID-19 Vaccines" (Appendix K) and a link to CDC's "Vaccines for COVID-19" page available at <https://www.cdc.gov/coronavirus/2019-ncov/vaccines/index.html>. Access to vaccines will follow routine practices and will depend on a participants' tier/health department eligibility to get the vaccine as well as vaccine availability. Contact information for vaccination sites and any referrals will be given according to the normal practices at each site.

All participants will be asked sign release of information forms for study team members to obtain test results and vaccination records. Vaccination records will also be collected through participant self-report (participants can show study staff their vaccination card). COVID test results and vaccine records will be collected as part of study data and will be needed to determine the effectiveness of the intervention.

- 7. **Social Network Referral** – Network referrals will be conducted as outlined above (See SNS Study condition). A study information card (Appendix D) will be given to all enrolled subjects to share with their network referrals. The information card contains information about the study and study team contact information. Linkages between study participants are collected through a code/code word process that our team has used in previous network referral studies.

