Other Important Variables: Age, race, ethnicity, gender, sex at birth, and CJI history; as well as COVID-19 knowledge, testing history, infection history, substance use history, beliefs around mask efficacy, treatment/prevention history, vaccine knowledge/attitudes, prior contact by contact tracer, experiences of racism, housing status, food insecurity, employment, experience of violence, workplace resources, PPE availability, and known COVID-19 contact.

Analytic overview. Two types of analyses will be performed.

The first will focus on the likelihood that a participant's network members are referred for testing. This will be modeled using logistic regression, with each network member treated as an observation (tested versus not). A three-level hierarchical model will be used, with random effects at the level of the study participant (level two) and the recruitment cluster (level three, all participants referred by the same index participant).⁴³ We shall also consider adding site as a fourth level to permit us to estimate between-site variability both in the outcomes and in the effectiveness of the interventions.

The second analysis will focus on the total number of individuals referred by a participant for testing, including both network members and additional referrals not initially named as part of the participant's network. The total number of referrals will be modeled using negative binomial regression.⁴⁴ A random effect at the level of the recruitment cluster will again be included to capture potential within-cluster correlation in the number of referrals. To ensure correct inferences even in cases where our models do not fully capture the within-cluster correlation in the data, we shall use the clustered version of the robust (i.e., sandwich) variance estimator throughout.⁴⁵

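### Network-member eligibility is worded relative to the index, so as written second-degree members must know the seed and attend within 14 days of the seed's visit, which conflicts with the referral design

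*Combined protocol and SAP*

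**What the plan says.** - **Who the list covers.** Under Recruitment of Index and Network Member study participants, seeds meet the index criteria, "while the first and second-degree network members will meet the social network member eligibility".
- **The list.** Under Inclusion and exclusion criteria, social network criterion (1) requires a member to be "linked to the index as a" friend, relative, colleague or regular contact. Criterion (2) requires a "visit within two weeks of index visit".
- **What *index* means.** The recruitment section treats index seeds as 12% of the sample and has indexes refer first-degree members, who then refer second-degree members. Study Visit Procedures, item 3 (Randomization) names the two groups separately: "Indexes and first-degree referrals will be randomized as described above". The Analytic overview defines a recruitment cluster as "all participants referred by the same index participant".
- **What eligibility controls.** People who "are eligible and provide the referral code can be enrolled in the study", so a referral who fails a criterion does not enter.
- **Whose contacts are sought.** The SNS Study Condition text (item 4) has staff ask each participant to refer people that participant regularly spends time with.
- **How the outcome is scored.** Primary Outcomes counts each participant's own network members tested. Attrition and missing data says every enrolled participant is analysed.

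**The concern.** Nothing in the protocol text gives second-degree members an anchor of their own. Two things follow if sites apply the criteria literally.

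First, a second-degree member must have a direct tie to the seed, although the design defines that person as a contact of someone the seed referred. Second, the clock starts at the seed's visit, so part of a first-degree participant's referral window has gone before that participant is enrolled.

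First-degree participants are themselves randomised and scored on the referrals they bring in. Turning away valid second-degree referrals therefore lowers their yield in both arms and shrinks the absolute difference between arms. If some sites follow the wording and others the likely intent, yield will also vary by site for reasons unrelated to messaging, and the plan intends to examine differences across sites.

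**Working it through.** **1. Window by type of referrer.** A seed's referrals have 14 days. A first-degree participant seen on day d after the seed has 14 − d days: 14 if seen on day 0, 7 on day 7, none on day 14.

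**2. The plan's own power figure.** Inputs from Power calculations: 0.44 versus 0.52, two-sided 0.05, network size negative binomial with mean 4 and SD 2.8, capped at 6 (mean after capping 3.53), and a participant-level intraclass correlation of 0.46. At the expected two referrals each, 300 seeds and 600 first-degree members refer, giving 900 referrers, 450 per arm.

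- Variance factor: 0.46 + 0.54/3.53 = 0.613.
- SE = √[(0.44×0.56 + 0.52×0.48) × 0.613 / 450] = 0.0260.
- Power = Φ(0.08/0.0260 − 1.96) ≈ 87%.

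This leaves out the cluster correlation of 0.37, so it shows that 87% is attainable on these inputs, not that it is the sponsor's calculation. The simulation is not specified fully enough to reproduce uniquely.

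**3. SE used below.** Solving the stated 87% for the SE: 0.08/(1.960 + 1.126) = 0.0259. It is held fixed in step 5.

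**4. Share of second-degree visits kept by the clock.** The documents give no distribution for referral lag, so these are assumptions. Take two independent lags (seed to first-degree, first-degree to second-degree), each within 14 days, and find the chance that their sum is at most 14. For exponential lags of mean μ truncated at 14 days, with a = 14/μ:

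k = [1 − e^(−a)(1 + a)] / (1 − e^(−a))²

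For lags uniform over 14 days, k = 0.5.

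**5. Contrast and power.** Assume that excluded referrals count as not tested and that only seeds (one third of referrers) and first-degree members (two thirds) refer. Then contrast = 0.08 × (1/3 + 2k/3), and power = Φ(contrast/0.0259 − 1.96).

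| Lag assumption | k | Lost | Contrast | Power |
|---|---|---|---|---|
| No restriction | 1 | 0 | 0.080 | 87% |
| Exponential, mean 3 days | 0.965 | 4% | 0.078 | 85% |
| Exponential, mean 5 days | 0.872 | 13% | 0.073 | 81% |
| Exponential, mean 7 days | 0.794 | 21% | 0.069 | 76% |
| Uniform, 0 to 14 days | 0.500 | 50% | 0.053 | 54% |

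**6. Cross-check.** A clustered simulation of seed, first-degree and second-degree chains, with participant-level randomisation, nested intraclass correlations and uniform lags, gave 85% with the clock set to the referrer and 56% with it set to the seed (300 seeds). With 377 seeds the figures were 92% and 66%. The absolute levels depend on how the unspecified parts of the simulation are filled in. The drop has a similar size to that in the last row of the table.

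**7. Tie rule.** The documents do not say what share of second-degree contacts also know the seed, so no estimate can be derived.

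**The case against.** **Intent.** The strongest reply is that this is loose drafting. A second-degree member is by definition someone whom a first-degree member refers, so requiring a tie to the seed would largely defeat the category. Criterion (1) is phrased in the second person, and staff use the same phrase with each referring participant. Enrolment runs on the referrer's own code. Power calculations also appears to use *index participants* loosely. This reading of intent is probably right. It does not change the written criteria, which many sites under two IRBs must apply: a site that follows the intent enrols people who fail a stated criterion.

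**Scoring.** The documents do not say that a referral who fails the tie or the window but is tested anyway is scored as not tested, or that such a person stays in the denominator. This objection stands, and the power figures are conditional on it.

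**Who refers.** Item 3 (Randomization) says second-degree members are not asked for referrals once the sample size is reached, which implies that they may be asked before then. The two-thirds share is therefore an assumption.

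**Stronger readings that do not hold.** A reader might infer a severe loss of power. That needs slow lags such as the uniform case; with exponential lags of mean 3 to 7 days the loss is about 2 to 11 percentage points. A reader might infer that the third wave would be starved and enrolment would fail. The plan lists other recruitment routes that could add seeds, and second-degree members may refer. A reader might infer bias between arms. Randomisation is per participant, so the days left at randomisation do not depend on that participant's own arm.

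**Conclusion.** The point holds as a fault in the written criteria. The eligibility wording contradicts the referral procedure and introduces a limit that the power simulation does not describe. Applied literally, it lowers first-degree participants' referral yield and dilutes the contrast.

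The size cannot be fixed from the documents. The clock alone costs little if referral is fast (87% to about 85% at a mean lag of 3 days) and a good deal if it is slow (about 54% for uniform lags). These figures rest on assumed lags, on excluded referrals being scored as not tested, on referral by seeds and first-degree members only, and on an SE back-calculated from the stated 87%. The tie rule would add to the loss by an unknown amount. A figure beside the criteria and the site appendix were not available; if either already sets the anchor to the referrer, the main text still needs to agree with it.

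**What to change.** In social network criteria (1) and (2), replace the index with *the participant who referred them*, and the index visit with *that participant's visit*. The criteria then match the referral design, and every referrer has the same 14-day window.

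The cost is a short protocol amendment. It needs no new procedure, because referral codes already link each person to a referrer. The downside is that recruitment within a seed's tree may run up to two weeks longer.
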